Impact of a Family History of Hypertension and Physical Activity on Left Ventricular Mass

NCT05334355

3/14/2023

Participants:

The experimental protocols and the process for obtaining informed consent conformed with the Declaration of Helsinki and were approved by the Institutional Review Board of Montclair State University. Informed consent was obtained from all participants included in the study prior to the start of data collection. All participants were recruited in and around the Department of Exercise Science and Physical Education. Participants were separated into two groups dependent on their self-reported FHH status. Participants also self-reported physical activity behavior. Physical activity was reported as the number of days per week performing moderate and/or vigorous physical activity for at least 10 minutes for recreation. Participants were excluded from the study if they reported any prior cardiovascular diagnoses.

Experimental Protocol

Participants were asked to fast (water allowed) for 4hr, abstain from caffeine for 12hr, and avoid alcohol, over-the-counter drugs, and exercise 24hrs prior to data collection. During this visit, BP, heart rate (HR), and mean arterial pressure (MAP) were recorded (Omron BP785N Blood pressure monitor, Lake Forest, IL, USA). The average of three measurements was recorded after ≥ 5 minutes of rest in the supine position. Height and weight were collected (Detectco, Webb City, MO, USA) and used to calculate BSA; $BSA = 0.007184 \times \text{weight}_{\text{kg}}^{0.425} \times \text{height}_{\text{cm}}^{0.725}$ (Du Bois, 1916).

Echocardiographic assessments were made while participants rested in the left lateral decubitus position. All measurements were made using a GE Vivid i Ultrasound (GE healthcare, Jiangsu, China) with a 2-5-MHz cardiac transducer. Participants underwent an echocardiogram using the parasternal long axis view, apical four chamber, and apical two chamber views according to the American Society of Echocardiography [2,3]. Briefly, the parasternal long axis view was done with the probe placed near the 3rd intercostal space adjacent to the sternum. Linear measurements of wall thicknesses and ventricular chamber diameter were measured using two-dimensional brightness mode ultrasound and were assessed just below the level of the mitral valve leaflet tips perpendicular to the LV long axis. End-diastole was defined as the first frame after the mitral valve closes. End systole was defined as the last frame before the mitral valve opened. LVM was calculated at end-diastole as $LVM = 0.8 \times 1.04 \times [(IVS + LVID + PWT)^3 - LVID^3] + 0.6$; where IVS is interventricular septum, PWT is posterior wall thickness, and LVID is left ventricular internal diameter [3]. Relative wall thickness (RWT) at end-diastole was calculated as $RWT = (2 \times PWT) / LVID$ [3]. Percentage fractional shortening (FS) was calculated as $100 \times [(LVID_{\text{Diastole}}$

– $LVID_{Systole} / LVID_{Diastole}$] [3]. Aortic diameter was measured at the aortic annulus during peak systole in the parasternal long axis view and was used to estimate aortic area using the following formula: $CSA = D^2 \times 0.785$ [2]. Apical views were done with the probe placed near the 5th or 6th intercostal space on the body's flank. Left ventricular volumes at end-diastole and end-systole were assessed using the modified Simpson's method of biplane disk summation [3]. Ejection fraction (EF) of the left ventricle was calculated as $EF = [(EDV - ESV) / EDV] \times 100$; where EDV is end-diastolic volume, and ESV is end-systolic volume [3]. Stroke volume (SV) was calculated as $SV = EDV - ESV$. Cardiac output (Q) was calculated as $Q = SV_{L/min} \times HR$. MAP was calculated as $MAP = [(1/3) \times SBP] + [(2/3) \times DBP]$; where SBP is systolic blood pressure, and DBP is diastolic blood pressure. Total peripheral resistance (TPR) was calculated as $TPR = MAP / Q$.

Statistical Analysis

Normality was tested using the Shapiro-Wilk test where significance ($p < 0.05$) indicated a non-normal distribution. Both LVM and LVM/BSA violated the Shapiro-Wilk test of normality. Simple bivariate comparisons between groups were made using unpaired t-tests for normally distributed variables, and Mann-Whitney tests when normality was violated. Effect sizes for bivariate comparisons were estimated using Cohen's d with 95% confidence intervals. Spearman's rank correlations coefficient (ρ) was used to examine relationships within each group and for all participants and variables of interest vs. LVM and LVM/BSA. ANCOVA tests were used to examine LVM and LVM/BSA compared between groups while statistically controlling for covariates of interest. LVM and LVM/BSA were logarithmically transformed prior to the ANCOVA investigations. The ANCOVA models were as follows. In model 1, age, SBP and sex were selected as common participant characteristic covariates that impact LVM and LVM/BSA. Model 2 accounted for the days per week of moderate-intensity exercise. Model 3 accounted for the days per week of vigorous-intensity exercise. Model 4 covariates included EDV and TPR as indices of preload and afterload. A significant probability value ($p < 0.05$) within the ANCOVA model for FHH status was interpreted as finding between-group differences when statistically controlling for the covariate variables. A lack of FHH significance in the model was interpreted as FHH status does not impact LVM or LVM/BSA independently of the covariate variable(s) within the model. Data is expressed as mean \pm SD. The alpha level for significance was set at $p < 0.05$. All statistical tests were performed using JASP version 0.14.1 (University of Amsterdam, Amsterdam, The Netherlands).

Data Availability

Data is available on the Montclair State University Digital Commons website at:
<https://digitalcommons.montclair.edu/data/10>

References

1. Du Bois D. Clinical Calorimetry. *Arch Intern Med.* 1916;XVII:863.
<http://linkinghub.elsevier.com/retrieve/pii/S089473170245599X>

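### FHH comparisons of the size-dependent supporting variables (EDV, ESV, SV, Q, TPR, aortic area) are unadjusted and un-indexed, so any difference in sex or size mix between groups could pass for an FHH effect

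*Combined protocol and SAP*

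**What the plan says.** Groups are observational: "Participants were separated into two groups dependent on their self-reported FHH status" (Participants). Participants were recruited in and around one department, and no matching or stratification is described.

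The Experimental Protocol section derives EDV, ESV, SV (EDV minus ESV), Q (SV times HR), TPR (MAP divided by Q) and aortic area (0.785 times diameter squared). None is divided by BSA. BSA is calculated from height and weight, but LVM/BSA is the only indexed quantity named.

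The Statistical Analysis section has two routes for comparing groups:

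- Unadjusted: "Simple bivariate comparisons between groups were made using unpaired t-tests for normally distributed variables, and Mann-Whitney tests when normality was violated", with Cohen's d and its 95% confidence interval as the effect size.
- Adjusted: "ANCOVA tests were used to examine LVM and LVM/BSA compared between groups while statistically controlling for covariates of interest". Of the adjustment sets, "In model 1, age, SBP and sex were selected as common participant characteristic covariates that impact LVM and LVM/BSA".

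EDV and TPR appear in the adjusted route only on the covariate side: "Model 4 covariates included EDV and TPR as indices of preload and afterload". The Spearman correlations relate variables to LVM and LVM/BSA and adjust no group comparison.

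**The concern.** The plan accepts that age and sex affect LV mass, and it indexes mass to BSA. It makes no such allowance for chamber volume, flow, resistance and aortic area measured in the same people. These quantities can be expected to vary with body size: a group with more men would tend to show larger EDV, SV, Q and aortic area and, because TPR has Q in its denominator, lower TPR.

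This matters because the plan itself names EDV and TPR as its preload and afterload indices. A reader who sees a group difference in either may take it as part of the mechanism linking FHH to LV mass. If it only reflects who is in each group, that reading is wrong. Cohen's d from the same raw comparison carries the same bias.

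**Working it through.** The documents give no group sizes, sex split or standard deviations, so there is no stated figure to reproduce. The calculations below illustrate the mechanism on assumed inputs, with a true FHH effect of zero throughout and two-sided testing at the plan's 0.05 level (the plan does not state sidedness).

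**1. Size of the spurious difference.** Assume BSA is 16% higher in men and EDV is proportional to BSA, plus a further 8% in men. The male-to-female EDV ratio is 1.16 × 1.08 = 1.253. The raw group means then differ by:

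- 60% versus 40% men: (1 + 0.6 × 0.253)/(1 + 0.4 × 0.253) − 1 = about 4.6%.
- 65% versus 35% men: (1 + 0.65 × 0.253)/(1 + 0.35 × 0.253) − 1 = about 7.0%.

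The 16% can be checked against the plan's own BSA formula: an assumed 80 kg, 178 cm person has 1.98 m² and a 65 kg, 165 cm person 1.72 m², a ratio of 1.15.

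**2. False rejection rates by simulation.** Further assumptions: within-sex BSA spread 9%, residual SD 12–28%, 30 or 50 per group. The adjusted model has log EDV as outcome, with FHH, age, sex and log BSA. Sex counts are fixed except in the last row.

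| Men in the two groups | Raw t-test | Adjusted model |
|---|---|---|
| 40% / 60% | about 7–18% | about 5% |
| about 35% / 65% | about 13–48% | about 5% |
| exactly equal counts | about 1–4% | about 5% |
| each person's sex drawn at random, 50% in both groups | about 5% | about 5% |

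Within the unbalanced rows, the rate rises with group size and falls as residual SD grows. Rounding also matters: 35% and 65% of 50 are 17.5 and 32.5. The top of the second row is 17 versus 33 men at the smallest SD; 18 versus 32 gives about 35% there.

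**3. A second, simpler model.** Let the sexes differ by d within-sex SDs and the male share differ by Δp around 50%. The spurious standardised difference is d·Δp/√(1 + d²·mean[p(1−p)]). With d = 1 and Δp = 0.2 this is 0.2/√(1 + 0.24) = 0.18. With 30 per group the standard error is √(2/30) = 0.258, and the normal approximation gives 10.7% rejection. Over d = 0.5–1.5, Δp = 0.1–0.3 and 20–50 per group, the range is 5.3% to 44.8%.

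That approximation treats sex counts as random around the stated shares. With counts fixed and d = 1, simulation gives:

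- 18 versus 12 men of 30: 7.7% raw, 5.0% with sex as covariate.
- 20 versus 10 of 30: 18.3% raw, 4.9% adjusted.
- 32 versus 18 of 50: 21.8% raw, 4.7% adjusted.

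Both models agree on direction and on the remedy.

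**The case against.** The strongest reply is that the study's question is LV mass. The rule for interpreting the FHH term concerns LVM and LVM/BSA only, the other tests are already called simple and bivariate, and nothing says a raw EDV or TPR difference will be read as an FHH effect. This stands as a limit on consequence: the comparisons are supporting. The plan also does not list which variables receive bivariate tests; their inclusion is inferred from the general wording and from their being measured.

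The second reply is that the inflated rates are conditional on an imbalance nobody has shown. This also stands. If sex is unrelated to FHH, the raw test averages about 5%. By chance alone a gap of at least 20 points in male share occurs about 16% of the time with 30 per group and 6% with 50; a gap of at least 30 points, about 2.7% and 0.4%. The rates also depend heavily on the assumed SD. What remains is that in an observational comparison nothing in the design protects the balance, and the realised mix is what a given raw difference must be read against.

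A reader might infer more than the documents support:

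- That the groups do differ in sex or size, or that a reported difference is spurious. No sex split or BSA by group is given.
- That the size argument covers every variable. Indexing does not apply to blood pressure, where the gap is adjustment for age and sex. It is weak for EF, FS and RWT, which are ratios.
- That the raw tests must be dropped. That is a preference; clear labelling is enough.

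**Conclusion.** The concern holds for EDV, ESV, SV, Q, TPR and aortic area: the plan offers no adjusted or indexed FHH comparison for them, although BSA is calculated and age and sex are used elsewhere in the plan. How far any actual result is affected cannot be judged from the documents. The inflation in the working requires an unequal sex or size mix and rests on assumed sex effects, SDs and group sizes. Where sex counts happen to be equal there is no false FHH signal; the cost is lost precision, because sex and size variation stays in the error term. The change is worth making because it is cheap and removes an ambiguity about the plan's own preload and afterload indices. It does not bear directly on the LVM and LVM/BSA analyses.

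**What to change.** For EDV, ESV, SV, Q, TPR and aortic area, add the FHH difference with 95% CI from a linear model on the log scale with FHH, age, sex and log BSA, reported as a ratio of geometric means. Base any FHH interpretation of these variables on that estimate. For blood pressure, adjust for age and sex only. Report sex and BSA by group, state which variables receive bivariate tests, and keep those comparisons and their Cohen's d labelled as unadjusted.

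The cost is a short addition to the Statistical Analysis section and a few model runs on data already held. Some raw differences may no longer be significant.

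### A non-significant FHH term in the log-scale ANCOVAs is read as no independent effect, with no adjusted estimate or interval stated to support that reading

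*Combined protocol and SAP*

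**What the plan says.** All of this is in the Statistical Analysis section of the combined protocol and SAP.

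- **Unadjusted comparisons.** "Simple bivariate comparisons between groups were made using unpaired t-tests for normally distributed variables, and Mann-Whitney tests when normality was violated". As "Both LVM and LVM/BSA violated the Shapiro-Wilk test of normality", both outcomes go to Mann-Whitney. The effect size is given in one sentence: "Effect sizes for bivariate comparisons were estimated using Cohen's d with 95% confidence intervals".
- **Adjusted comparisons.** "LVM and LVM/BSA were logarithmically transformed prior to the ANCOVA investigations". Model 1 adjusts for age, SBP and sex, Model 2 for days of moderate exercise, Model 3 for days of vigorous exercise, and Model 4 for EDV and TPR.
- **Reading the models.** A p-value below 0.05 "within the ANCOVA model for FHH status was interpreted as finding between-group differences" after adjustment. In the other direction, "A lack of FHH significance in the model was interpreted as FHH status does not impact LVM or LVM/BSA independently" of whatever covariates that model contains. The qualifier matters: the plan denies an effect beyond the covariates, not any effect at all.

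The plan names no adjusted FHH difference, ratio or confidence interval for Models 1 to 4. No sample size, power, target difference or equivalence margin appears anywhere in the document.

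**The concern.** The second half of the reading rule turns failure to reject into a finding of no independent effect. A p-value at or above 0.05 arises both when the adjusted difference is close to nil and when the study is too imprecise to tell. The rule draws the first conclusion in either case, and nothing stated for the adjusted models lets a reader tell the two apart. The Cohen's d interval does not help, because it belongs to the unadjusted comparisons and the rule applies to the adjusted ones.

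The rule governs four models and two outcomes, 4 × 2 = 8 FHH terms, and those terms carry the study's answer on whether family history matters beyond the covariates. A wrong statement of no independent impact would therefore be a wrong headline result.

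**Working it through.** The plan has no figure to reproduce, because it states no sample size, SD or target effect. The numbers below show what the rule could do under assumed inputs.

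**Assumed inputs (none from the documents).** Equal groups of 20 to 50; residual SD of log LVM 0.15 to 0.25; variance inflation (VIF) from correlation between FHH and the covariates 1.0 to 1.2; true adjusted ratios of geometric means 1.10 and 1.15. Alpha is 0.05 as in the plan. The plan does not state sidedness, so two-sided is assumed.

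**Formulas.**
- SE of the log ratio = residual SD × √[(1/n₁ + 1/n₂) × VIF]
- df = n₁ + n₂ − 2 − k, with k covariates
- 95% CI at an estimated ratio of exactly 1.00 = exp(± t × SE)
- Probability of non-significance from the noncentral t with noncentrality ln(ratio)/SE

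**One case in full: 30 per group, residual SD 0.20, VIF 1.2, k = 3.**
- SE = 0.20 × √[(2/30) × 1.2] = 0.0566
- df = 60 − 2 − 3 = 55, so t = 2.004 and t × SE = 0.113
- CI = exp(−0.113) to exp(0.113) = 0.893 to 1.120
- For a true ratio of 1.10, noncentrality = 0.0953/0.0566 = 1.68, and non-significance has probability 0.619. For 1.15 it is 0.1398/0.0566 = 2.47 and 0.320.

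**Across the range.**

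| n per group | residual log SD | VIF | 95% CI at estimate 1.00 | non-significant at true 1.10 | at true 1.15 |
|---|---|---|---|---|---|
| 50 | 0.15 | 1.0 | 0.942–1.061 | 0.118 | 0.004 |
| 30 | 0.20 | 1.0 | 0.902–1.109 | 0.558 | 0.242 |
| 30 | 0.20 | 1.2 | 0.893–1.120 | 0.619 | 0.320 |
| 20 | 0.25 | 1.2 | 0.839–1.192 | 0.812 | 0.652 |

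In the first row a null estimate excludes ratios above about 1.06, and a near-null statement would be fair. In the last row the same p-value is compatible with a 19% increase. The plan's rule gives both the same conclusion.

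**Check by simulation.** Ten thousand ANCOVAs were simulated with 30 per group, residual SD 0.20 and three covariates, one correlated 0.35 with FHH. At a true ratio of 1.15 the FHH term was non-significant in 32.5%, and in 91.9% of those the 95% CI still included 1.15. At 1.10 the figures were 62.0% and 96.2%. In most of the cases where the rule would declare no independent impact wrongly, the interval would have kept the true value in view.

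**Is Cohen's d itself a problem?** For log-normal data with equal spread and a ratio of 1.15, raw-scale d against log-scale d is 0.548 vs 0.559 at log SD 0.25, 0.334 vs 0.349 at 0.40, and 0.211 vs 0.233 at 0.60. The mismatch with a rank test is real but small.

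**The case against.** **The plan makes a conditional statement, not a claim of no impact.** This is right, and the rule must be read with its qualifier. The qualifier narrows which effect is denied; it does not change that absence is inferred from a non-significant test.

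**Silence is not exclusion.** The section is a one-paragraph summary. The software may well have produced adjusted estimates, and a public data location is given. So the accurate statement is that none is stated, not that none exists. The reading rule, however, is stated, and it uses the p-value alone.

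**The magnitude is all assumption.** A range of 12% to 81% runs from ample to poor power. The figures show that an uninformative null is possible, not that it occurred here. That stands. It is also the reason to ask for an interval, since nothing else in the plan shows where this study lies.

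**A stronger reading is tempting.** A reader might infer that Cohen's d is invalid for LVM and LVM/BSA because "Mann-Whitney tests when normality was violated" are used for them, or that mean ± SD is wrong for skewed outcomes. The documents do not support either. An effect size need not share the scale of the test, the numerical gap is small when spread is similar, larger gaps need unequal spread that the documents do not show, and no planned test result changes. These are reporting preferences.

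**Conclusion.** The point holds as an unsound interpretation rule. Followed as written, it can declare no independent effect of FHH when the data are merely imprecise, and the plan states nothing for the adjusted models that would reveal this. At an assumed 30 per group and residual log SD 0.20, the rule would wrongly do so in 56% to 62% of studies with a true ratio of 1.10 and in 24% to 32% with 1.15. All of these rest on assumed group sizes, SDs and ratios; at 50 per group and SD 0.15 they fall to 12% and 0.4%.

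It would go too far to say that this study was underpowered, that FHH does have an independent effect, or that the planned tests are wrong. The documents support none of these. The change should be made, but it concerns wording and reporting and leaves every planned test in place. Confidence is medium, because the size depends on figures the documents do not give.

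**What to change.** 1. **Report the adjusted effect.** For each of Models 1 to 4 and each outcome, give the FHH effect as a back-transformed ratio of geometric means with 95% CI. Check the log-scale residuals first, because the plan reports no normality result after transformation. Label the ratios as added after the normality results were known.
2. **Replace the sentence on non-significance.** Suggested wording: *A non-significant FHH term is reported as no clear evidence of a difference given the covariates in the model, together with the range of ratios that the 95% confidence interval leaves open.*
3. **Qualify Model 4.** Describe its ratio as conditional on EDV and TPR, which may lie on the path from FHH to LVM, and not as the total FHH effect.

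**Optional only:** a rank-biserial correlation with 95% CI beside, not instead of, Cohen's d for rank-tested variables, and a median with quartiles or a geometric mean beside mean ± SD.

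**Cost:** revised SAP wording and a little extra output from models already planned, on existing data. The downside is that the ratios are only as good as the fit of the log scale.

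### Model 4 compares LV mass at a given chamber size, so a non-significant FHH term in it does not show that FHH has no effect on LV mass independent of preload and afterload

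*Combined protocol and SAP*

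**What the plan says.** All points are in the combined protocol and SAP.

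- **Outcome (Experimental Protocol).** LVM is computed at end-diastole from a difference of cubes, "IVS + LVID + PWT)^3 - LVID^3", "where IVS is interventricular septum, PWT is posterior wall thickness, and LVID is left ventricular internal diameter". The dimensions come from the parasternal long-axis view: "Linear measurements of wall thicknesses and ventricular chamber diameter were measured using two-dimensional brightness mode ultrasound".
- **EDV (Experimental Protocol).** "Left ventricular volumes at end-diastole and end-systole were assessed using the modified Simpson's method of biplane disk summation", from the apical views.
- **TPR (Experimental Protocol).** SV is EDV minus ESV. Cardiac output Q is SV times HR. TPR is MAP divided by Q.
- **Model 4 (Statistical Analysis).** "Model 4 covariates included EDV and TPR as indices of preload and afterload". The outcomes are log LVM and log LVM/BSA.
- **Reading rule (Statistical Analysis).** With alpha at 0.05, a significant FHH term is read as a group difference after controlling for the covariates. A non-significant one is read as FHH having no impact on LVM or LVM/BSA independently of the covariates in that model.

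The plan does not mention that EDV and LVM share the cavity, or that TPR is computed from EDV. It plans no check of either.

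**The concern.** EDV is offered as a measure of preload, but it is also a measure of how large the ventricle is, and ventricular size is part of the outcome. Adjusting for it fixes much of the chamber component of LVM and leaves mainly wall thickness to vary. Two readings could then go wrong:

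1. FHH is associated with a larger chamber and hence more mass. Model 4 shrinks the difference, the term may not reach significance, and the rule reports no independent impact.
2. FHH is associated with thicker walls and a smaller chamber, with total mass unchanged or slightly lower. Model 4 can show higher adjusted LVM.

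The adjustment cannot tell a chamber enlarged by preload from one enlarged for another reason. The afterload index does not avoid the difficulty, because EDV sits in its denominator.

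**Working it through.** The documents give no sample size, SD or expected difference, so there is no stated figure to reproduce. The formulas are the plan's; every number below marked as assumed is not.

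**Step 1. How much of LVM is cavity?** Assume IVS = PWT = 0.9 cm and LVID = 4.8 cm.

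- Baseline: 0.8 × 1.04 × (6.6³ − 4.8³) + 0.6 = 0.832 × (287.50 − 110.59) + 0.6 = 147.8 g.
- LVID +5% (5.04 cm), same walls: 0.832 × (6.84³ − 5.04³) + 0.6 = 160.3 g, or +8.5%.
- Walls +5% (0.945 cm), same LVID: +6.7%.
- Walls +5% and LVID −5% (4.56 cm): 0.832 × (6.45³ − 4.56³) + 0.6 = 145.0 g, or −1.9%.
- Walls 1.0 cm and LVID 4.4 cm: 147.8 g, the baseline mass, but RWT is 2 × 1.0/4.4 = 0.45 against 2 × 0.9/4.8 = 0.375.

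Over assumed ranges of LVID 4.2–5.4 cm and walls 0.7–1.1 cm, a 1% change in LVID changes LVM by about 1.56% to 1.75%, and a 1% change in wall thickness changes it by about 1.23% to 1.43%. Both components matter. Because the formula is a difference of cubes, LVM does not scale as LVID cubed.

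**Step 2. TPR in terms of EDV.** Substituting the plan's definitions, TPR = MAP / [(EDV − ESV) × HR]. At a given pressure, heart rate and ejection fraction, TPR falls as the chamber gets larger.

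**Step 3. What Model 4 does to the FHH term.** Simulation with 400,000 subjects. Assumed: log-normal LVID (SD 8%) and walls (SD 10%), EDV proportional to LVID³ with measurement error as shown, EF 0.60 (SD 0.04), HR 62 (SD 8), MAP 85 (SD 7), and no effect of load on mass. Model 4 is fitted with EDV and TPR as its only covariates.

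| EDV error | Cavity only, crude +8.5% | Concentric shift, crude −1.9% |
|---|---|---|
| 5% | +0.6% | +6.1% |
| 10% | +1.4% | +5.2% |
| 15% | +2.6% | +4.0% |
| 20% | +3.6% | +3.0% |
| 30% | about +5.2% | +1.3% |

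Entries vary by about 0.1 percentage point between runs. A wall-only effect is unchanged: about +6.7% both crude and in Model 4.

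**Step 4. The role of TPR.** Adding TPR to a model that already has EDV moves the FHH term by only about 0.1 percentage point. TPR without EDV still cuts the cavity-driven +8.5% to about +3.3% to +4.3% at 5–15% EDV error. The correlation of EDV with TPR is about −0.78.

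**Step 5. Effect on the test.** A second simulation assumed 30 per group, walls with CV 12%, and a +10% LVM effect (log difference about 0.095), with 3,000 runs per setting.

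- Effect through the cavity only: the rejection rate falls from about 40% unadjusted to 5%, 7%, 12% and 21% at EDV error of 5%, 10%, 20% and 30%. The coefficient becomes 0.006, 0.017, 0.040 and 0.059.
- Effect through the walls only: the coefficient stays at 0.096–0.099, and the rejection rate moves from about 39–43% to 44–56%.
- No FHH effect: Model 4 rejects 4.6–6.2% of the time.

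**The case against.** **Model 4 is a valid test.** This stands. A reader might infer that Model 4 cannot test anything about FHH and LV mass. The documents do not support that: walls vary at a fixed EDV, type I error is close to nominal, and a wall-mediated effect is kept in full. The fault lies in the conclusion drawn from the model.

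**EDV is not the LVID in the formula.** This also stands. They come from different views and methods, so the overlap is strong but not an identity, and no figure in the documents fixes how closely they agree. The results are therefore shown up to 30% error. The attenuation weakens but does not vanish.

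**Removing a preload path may be the purpose.** This stands in part. If FHH acts through volume load, taking that path out is what independence of preload means. But EDV removes any chamber-size path, loaded or not, and the simulation, which has no load effect at all, shows the same attenuation.

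**The rule speaks only of independence from the covariates.** Literally true. But the same section names those covariates as indices of preload and afterload, so a loading interpretation is the natural one.

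**TPR biases the FHH term.** A reader might infer this from the shared EDV. Once EDV is in the model, the calculation does not bear it out. The plan also interprets only the FHH term, so the sign of the TPR coefficient is not at issue.

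**Other analyses show the crude difference.** This stands. The unadjusted comparisons and Models 1–3 contain neither EDV nor TPR, and Model 1 already adjusts for SBP. This limits the consequence to Model 4's own conclusion.

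**Conclusion.** The concern holds as a limit on interpretation. Model 4 estimates the FHH difference in LVM at a given chamber size. A non-significant term there does not support the statement that FHH has no effect on LV mass independent of preload and afterload, and a significant one need not mean that total mass is higher.

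The direction follows from the plan's formulas. The size rests on assumed dimensions, variability and EDV error, and on EDV tracking LVID cubed apart from noise. Within 5–30% EDV error, between about 7% (0.6/8.5) and 61% (5.2/8.5) of a cavity-driven difference survives, and the concentric shift changes sign throughout. Sizes were worked out for LVM only. The same mechanism applies to LVM/BSA, since dividing by BSA does not take chamber size out of the numerator.

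The documents do not support going further and calling the study's overall finding on FHH wrong: they report no Model 4 result, and the other analyses are untouched by this point.

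**What to change.** In the Statistical Analysis section:

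1. Restate Model 4 as the FHH difference in LVM and LVM/BSA at a given chamber size, and say that EDV measures the cavity that enters LVM and that TPR is computed from EDV.
2. Withdraw the no-impact reading of a non-significant FHH term for this model.
3. Report FHH against RWT, which is already calculated, beside Model 4, so that a change in geometry can be told from a change in mass.
4. Add a sensitivity model that adjusts LVM and LVM/BSA for MAP, already obtained and not built from the LV cavity. It will overlap with the SBP adjustment in Model 1.

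Model 4 itself may be kept. Dropping EDV and TPR would give up the preload question altogether, which is a debatable trade. Entering EDV and TPR in separate models would not solve the problem, since TPR alone also attenuates a cavity-driven effect.

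The cost is wording and two further analyses on existing data. The plan already reports normality results, so the additions should be labelled as made after the data were seen. The downside is that the study no longer claims a clean adjustment for preload.

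### Model 4 for LVM/BSA adjusts a size-indexed outcome for un-indexed EDV and TPR with no BSA term, so the FHH effect can absorb a body-size difference between groups

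*Combined protocol and SAP*

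**What the plan says.** The Statistical Analysis section states that "ANCOVA tests were used to examine LVM and LVM/BSA compared between groups while statistically controlling for covariates of interest", and that "LVM and LVM/BSA were logarithmically transformed prior to the ANCOVA investigations". For the fourth model it states: "Model 4 covariates included EDV and TPR as indices of preload and afterload". As listed, that model contains no BSA, height, weight or sex. Sex appears only in Model 1, and the text does not say that covariates carry over from one model to the next.

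The Experimental Protocol section defines the covariates. EDV is a biplane Simpson volume that is not divided by BSA. Stroke volume is EDV minus ESV, and cardiac output Q is stroke volume times heart rate. "Total peripheral resistance (TPR) was calculated as" MAP over Q. No EDV/BSA, cardiac index or TPR index is defined. BSA itself is available: "Height and weight were collected (Detectco, Webb City, MO, USA) and used to calculate BSA".

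Under Participants, the groups are formed by self-reported FHH. The plan takes p below 0.05 for FHH as a between-group difference given the covariates. It takes a non-significant result as no FHH effect independent of them.

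**The concern.** In the LVM/BSA version of Model 4 the outcome and covariates are on different scales. A larger person tends to have a larger EDV and a lower TPR simply because of size. Two people with the same size-relative load but different BSA can therefore get different predicted LVM/BSA. If the FHH groups differ in BSA, part of that discrepancy can be credited to FHH.

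The groups are self-selected and no matching is described, so a BSA difference is possible. A sex imbalance would be one route to it. The decision rule is binary, so a shift of a few percent could create an apparent FHH effect or hide a real one, depending on which group is larger.

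The raw-LVM version has no such mismatch. Its weakness is different: body size is controlled there only indirectly, through EDV and TPR.

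**Working it through.** The documents give no sample size, SD, slope or group BSA, so there is no figure of the plan's to reproduce. The structure comes from the documents; all numerical inputs are assumptions.

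**Notation.** s = log BSA, EDV = EDVI × BSA, TPR = TPRI / BSA. b1 and b2 are the log-log slopes of mass on preload and afterload.

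**What Model 4 leaves out**

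- *Indexed-load structure.* If log(LVM/BSA) = b1·log EDVI + b2·log TPRI + error, substituting raw covariates gives b1·log EDV + b2·log TPR + (b2 − b1)·s + error. The omitted term is k·s with k = b2 − b1.
- *Absolute-load structure.* If log LVM = b1·log EDV + b2·log TPR + c·s + error, subtracting s gives an omitted term with k = c − 1.

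In both cases, bias in the FHH coefficient ≈ k × δ, where δ is the group difference in log BSA given EDV and TPR.

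**Assumed inputs.** SD of log BSA 0.11, of log EDVI 0.16, of log TPRI 0.18; residual SD 0.15; equal groups; raw EDV and TPR entered linearly; true FHH effect 0; 400,000 simulated subjects per setting. BSA gaps are 0.05 and 0.10 on the log scale (about 5% and 10%). Raw EDV and TPR already carry some size information, so δ is smaller than the gap: about 0.0273 and 0.0549.

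**Spurious FHH effect on LVM/BSA, 100·(exp(kδ) − 1)**

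| Structure | k | Gap 0.05: formula / simulated | Gap 0.10: formula / simulated |
|---|---|---|---|
| Indexed, b1 0.6, b2 0 | −0.6 | −1.6% / −1.6% | −3.2% / −3.2% |
| Indexed, b1 0.6, b2 0.2 | −0.4 | −1.1% / −1.1% | −2.2% / −2.1% |
| Indexed, b1 = b2 (0.3 or 0.6) | 0 | 0 / within 0.1% | 0 / within 0.1% |
| Absolute, c = 1 | 0 | 0 / within 0.1% | 0 / within 0.2% |
| Absolute, c = 0.5 | −0.5 | −1.4% / −1.3% to −1.4% | −2.7% / −2.6% to −2.8% |
| Absolute, c = 0 | −1 | −2.7% / −2.7% to −2.8% | −5.3% / −5.3% to −5.4% |

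With no gap the estimate was about zero in every structure. The negative sign applies to the group with the larger BSA.

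**Type I error at nominal 5%** (indexed structure, raw covariates, 4,000 replicates; assumed total N of 40 / 80 / 120)

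- b1 0.6, b2 0.2: 5.5% / 6.0% / 7.4% at gap 0.05; 6.8% / 9.0% / 11.3% at gap 0.10.
- b1 0.6, b2 0: 5.9% / 7.1% / 9.3% at gap 0.05; 10.1% / 13.7% / 18.5% at gap 0.10.

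The simulation standard error near 5% is √(0.05 × 0.95 / 4,000) ≈ 0.34 points, so the smallest of these are barely distinguishable from 5%. The absolute structure with c = 0, gap 0.10 and N = 60 gave 20.4%.

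**Candidate repairs**

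- *Indexed covariates only.* About zero bias under the indexed structure, but that follows by construction. Under the absolute structure with c = 1, the omitted term is (b1 − b2)·s over the full gap: 0.4 × 0.05 = 0.02 (+2.0%) and 0.4 × 0.10 = 0.04 (+4.1%). Simulation agrees. With c = 0 and b1 = b2 the bias is −4.9% and about −9.6%, worse than the plan's model.
- *Raw EDV and TPR plus log BSA.* Within 0.13% of zero in every setting above. Type I error was 4.4% to 5.8% across eight scenarios at N = 60.

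**Link between the two outcomes.** Since log(LVM/BSA) = log LVM − log BSA, least squares with the same covariates gives: FHH coefficient for LVM/BSA = that for LVM minus that for log BSA. Example (indexed, 0.6 and 0.2, gap 0.05): LVM +1.70%, BSA +2.79%; log(1.0170) − log(1.0279) = 0.0169 − 0.0275 = −0.0107, or −1.06%, as simulated. The +1.70% also shows body size entering the raw-LVM version. Once log BSA is a covariate, its own FHH coefficient is zero and the two outcomes give the same FHH coefficient.

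**The case against.** A reader might infer that the FHH effect is biased whenever the groups differ in size. The documents do not support that. A BSA gap is necessary but not sufficient: the bias vanishes when the load slopes are equal, when neither load matters under the indexed structure, or when mass is proportional to BSA at a given absolute load.

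A reader might also infer that this study's Model 4 result is biased. That is not shown either. BSA by group is not reported, so neither the existence nor the direction of a gap can be read from the text. At a gap of about 5% with moderate slopes the distortion of the test is small.

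The other side can also say that absolute versus size-relative load is a choice of estimand, and that simulating an indexed world and then finding indexed covariates unbiased is circular. Both points stand. They defeat indexing as the main remedy. They do not defeat adding log BSA, which held up under both structures.

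Finally, adding log BSA to the raw-LVM version changes its question and removes its distinct content. That also stands, and is a reason to keep the un-indexed model for description.

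**Conclusion.** The scale mismatch in the LVM/BSA version of Model 4 is certain from the text; its effect is conditional. For assumed BSA gaps of about 5% to 10%, the FHH coefficient can be off by roughly 1% to 5% of LVM/BSA, with type I error between about 5.5% and 20% depending on the gap, slopes and sample size. It is about zero with no gap or in the offsetting cases above. All slopes, SDs, gaps and sample sizes are assumptions, and actual bias is not shown. The analysis also reads Model 4 as listed. If sex or other Model 1 covariates were carried forward, part of any size gap would already be absorbed.

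This is separate from whether EDV and TPR should be adjusted for at all. It is worth acting on because the remedy is cheap, not because the result is known to be wrong.

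**What to change.** 1. Report BSA (mean and SD) by FHH group.
2. Add log BSA to Model 4 beside EDV and TPR, and take the FHH result from that model.
3. Fit LVM/BSA with EDV/BSA and TPR × BSA only as a sensitivity analysis, because indexing alone is biased if mass follows absolute load.
4. Keep the un-indexed LVM model (EDV and TPR, no BSA) for description, stating that body size is controlled there only through EDV and TPR.

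No new measurements are needed, since BSA is already calculated from height and weight. The cost is one degree of freedom. In addition, the FHH coefficient becomes algebraically identical for log LVM and log LVM/BSA, so the two should be reported as one result. The analysis section is written in the past tense, so the change would be a re-analysis and should be labelled as such.
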